## Table 4. Dose Modifications

Common Terminology Criteria (CTCAE) Version 4.0	Adverse Event	Dose Change for Pomalidomide
Cardiac Arrhythmia	Grade 2	Hold study drug until resolved to < Grade 1; Decrease dose by 1 dose level
Cardiac Arrhythmia	Grade 3 or 4	Discontinue study drug
Prolonged QTs Interval	Grade 3 (>0.50 second)	Hold study drug; decrease dose by 1 dose level and restart when resolved to < Grade 2
Prolonged QTs Interval	Grade 4 (>0.50 second, life threatening symptoms)	Discontinue study drug
Vascular	Thrombosis/embolism - Grade 2, 3 or 4	Discontinue study drug
Dermatology/ Skin	Rash non-desquamation - Grade 3	Hold study drug until resolved to < Grade 1. Decrease dose by 1 dose level
Dermatology/ Skin	Rash non-desquamation - Grade 4	Discontinue study drug
Dermatology/ Skin	Rash / desquamation - Grade 3, 4	Discontinue study drug
	Rash / desquamation - Grade 2	The dose may be modified or discontinued at the investigators discretion.
Dermatology/ Skin	Rash Erythema multiforme	Discontinue study drug
Endocrine	Elevated or Reduced Thyroid Function Test results without symptoms of hyper- or hypo- thyroidism	Confirm test results and if significant, refer for therapy; Do not alter study drug regimen

Common Terminology Criteria (CTCAE) Version 4.0	Adverse Event	Dose Change for Pomalidomide
Endocrine	Elevated or Reduced Thyroid Function Test results with symptoms of hyper- or hypo- thyroidism	Hold study drug; Evaluate etiology and refer for appropriate therapy; Restart at the prior dose once symptoms have resolved and thyroid function has been stabilized with medical and/or surgical intervention
Neurology	Neuropathy cranial/motor/ sensory - Grade 2	Hold study drug; Restart at same or 1 dose level lower once event has resolved to < Grade 1
Neurology	Neuropathy cranial/motor/ sensory Grade 3 or recurrence of Grade 2	Hold study drug until resolved to < Grade 1; Decrease dose by 1 dose level
Neurology	Neuropathy cranial/motor/ sensory - Grade 4	Discontinue study drug
Other pomalidomide related toxicity	Grade 3 or Grade 4	Hold pomalidomide therapy; Decrease dose by 1 dose level and restart when resolved to < Grade 2

## 3.4 QUESTIONNAIRES

Patient self-report questionnaires administered in this study are part of the standard NIH chronic consensus recommended criteria for the evaluation of cGvHD in clinical trials. These standardized assessments are designed to evaluate patient quality of life (SF-36, FACT-BMT), functional performance (HAP) and symptoms (Lee symptom scale, symptom intensity scale). The purpose of these evaluations is to assess the potential benefit of the administered therapy as compared to the baseline. These forms have been extensively used, published and validated. These forms are also standard part of many NCI CCR cGvHD protocols (Appendix G). In a recent study median time for persons to complete these forms was 15 minutes (range 8-22 minutes).

## 3.5 STUDY CALENDAR

Assessments	Screening	BL						3		6		9		
		BI/	C1	C2	$C^{2}$	C3	C3	mos	C5.6	mos	C80	mos C10	C11	C12
		C1	D15	D1	D15	D1	D15	D1	D1	D1	D1	D1	12	D28
		D1	(+/-2	(+/-2	(+/-2	(+/-2	(+/-2	(+/-3	(+/-2	(+/-3	(+/-2	(+/-3	D1	(+/-3
			days)	days)	days)	days)	days)	days)	days)	days)	days)	days)	(+/-2 days)	days)
Informed Consent	Х													
Randomization	Х													
Pomalidomide po qd 		Х	Х	Х	Х	Х	Х	X	X	X 				
History and Physical Exam	Х	Х	Х	Х	Х	Х	Х	Х	Х	Х	Х	Х		Х
Confirmation of cGvHD 	Х													
Body Photography		Х								Х				
cGVHD 3 Month Trajectory (stable vs.		Х												
progressive)								37		37		37		
Testing	X							X		X		X		Х
Diagnostic Imaging 	Х							Х		Х		Х		
Pregnancy Test 	Х	Х	Х	Х		Х		Х	Х	Х	Х	Х	Х	
POMALYST REMS ™ program 	Х	Х		X		Х		X	X	Х	X	Х	Х	Х
cGvHD Therapies Recording	X	Thro	oughout	the stu	dy									

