#### 2.3 SCREENING EVALUATION

Screening procedures may be performed on a CCR screening protocol, most commonly on 04-C-0281 "Natural History of Chronic GVHD." All studies must be completed within 8 weeks prior to enrollment:

- History and physical exam, Karnofsky performance score
- Documentation of cGvHD diagnosis, NIH organ and global severity stage
- CBC, platelets, differential, PT/PTT, serum chemistries (including sodium, potassium, chloride, CO2, calcium, magnesium, phosphorus, blood urea nitrogen [BUN], creatinine, glucose, albumin, total protein, alkaline phosphatase, total bilirubin, AST [SGOT], ALT

[SGPT], lactate dehydrogenase [LDH], and uric acid), urinalysis, urine pregnancy testing, TSH

- Infectious serology markers (HIV-1, HBV, HCV)
- Determination of estimated creatinine clearance
- Pulmonary function testing, CT of the chest (BOS sequence), cardiac ECHO, ECG
- Social work screening consult

For baseline evaluations, please see Section 2.6.

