## 2.4 **REGISTRATION PROCEDURES**

Authorized staff must register an eligible candidate with NCI Central Registration Office (CRO) within 24 hours of signing consent. A registration Eligibility Checklist from the web site (http://home.ccr.cancer.gov/intra/eligibility/welcome.htm) must be completed and sent via encrypted email to: NCI Central Registration Office (HOIS) <[contact]. After confirmation of eligibility at Central Registration Office, CRO staff will call pharmacy to advise them of the acceptance of the patient on the protocol prior to the release of any investigational agents. Verification of Registration will be forwarded electronically via email to the research team. A recorder is available during non-working hours.

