#### **Randomization and Arm Assignment**

Randomization will be done at the time of enrollment by the Central Registration Office, which will perform the randomization using randomization assignments determined by the study statistician. Subjects will be randomized to one of two treatment arms: low dose (0.5 mg/d) and high dose (0.5, escalating every two weeks to 1.0. 1.5 or 2.0 mg/d) pomalidomide. If one of the arms closes due to futility, toxicity or completion, enrollment will continue to the remaining arm.

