#### 2.6 **BASELINE EVALUATION**

Following studies will be performed at the baseline before/after the enrollment and within four weeks prior to starting taking the study drug unless otherwise indicated below:

- History and physical exam, Karnofsky performance score
- CBC, platelets, differential, PT/PTT, serum chemistries (including sodium, potassium, chloride, CO2, calcium, magnesium, phosphorus, blood urea nitrogen [BUN], creatinine, glucose, albumin, total protein, alkaline phosphatase, total bilirubin, AST [SGOT], ALT [SGPT], lactate dehydrogenase [LDH], and uric acid), CRP, total complement and C3 and C4, urine pregnancy testing (once within 10-14 days prior to the start of study drug and again within 24 hours prior to the start of study drug), immunoglobulin levels, TBNK, blood CMV PCR, drug levels if pertinent (e.g., cyclosporine, tacrolimus, sirolimus)
- MRI of the involved extremity if clinically indicated (acceptable if done within 8 weeks)
- Documentation of cGvHD per NIH criteria (diagnostic, distinct, other and common manifestations), NIH organ and global stage, baseline assessments (form A and form B) per NIH response criteria, date of cGvHD diagnosis, prior and current treatments, prednisone or other steroids oral dose, and other patient, donor and transplant characteristics per Appendix Q.
- Specialty evaluations of cGvHD: dermatology, ophthalmology, dental, rehabilitation and occupational therapy, gynecology if applicable (can be done up to two weeks after starting study drug, except for dermatology and dental evaluations which must be done prior to starting study drug)
- Diagnostic and research biopsies of the skin and mouth (all persons), and other organs (only if clinically indicated)
- ECG
- Research laboratory (blood, saliva, urine)
- Study drug dispensation
- Subject diary review
- Documentation of concurrent medications

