## **3 STUDY IMPLEMENTATION**

#### 3.1 STUDY DESIGN

The study is a randomized phase 2 trial with the single stage selection design. It is known from prior trials that the maximum tolerated dose of pomalidomide is about 3 mg/d in persons with bone marrow disorders receiving prior therapies for cancer, in cGvHD doses <3mg/d have been well tolerated. This study will explore clinical toxicity of gradual escalation of pomalidomide doses <3 mg/d in subjects with cGvHD. Patients will receive either a constant low dose of pomalidomide (0.5 mg/day) for six months or a strategy of increasing dose of pomalidomide from 0.5 mg/d up through each individual patients' maximum tolerated dose, with escalations by 0.5 mg/d every 2 weeks to a maximum of 2.0 mg/d. In each of the two arms, the trial will use a single stage design.

As an early stopping rule for futility as outlined in section **8**, if after 7 patients have enrolled on either arm, 0 have responded, then no further patients will be accrued to that arm as soon as this can be determined. To protect patient safety, an early stopping rule will be implemented. With two arms, each of which has a maximal accrual of 16 patients, up to 32 evaluable patients will be randomized. Safety assessments and pregnancy testing for FCBP will be performed at scheduled intervals as described in the Study Calendar.

Response will be assessed every 3 months while taking pomalidomide following the criteria in Section 6.2. The primary efficacy endpoint will be evaluated at 6 months. Efficacy outcome is defined as clinical response (CR or PR) in subjects who enter the study with stable cGvHD or stable disease for  $\geq$ 3 mo for subjects with progressive cGvHD at study-entry. (Stability will be assessed by the clinician and by the clinical exam at the screening evaluation based on the clinician estimate of the disease trajectory during the 3 months pre-randomization). Subjects who meet the response criteria at 6 months will continue therapy for another 6 months. If in the subject's best interest, efforts will be made to provide access to study drug on compassionate basis beyond the 12-month study endpoint.

Patients who discontinue therapy for any reason will be followed for up to 24 months after starting pomalidomide as described in Section **6.1.3**.

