#### **Abbreviated Title:** Pomalidomide for cGvHD **Version Date:** 4/29/2025

Assessments	Screening	BL						3		6		9		
								mos		mos		mos		
		BL/	C1	C2	C2	C3	C3	C4	C5,6	C7	C8,9	C10	C11,	C12
		C1	D15	D1	D15	D1	D15	D1	D1	D1	D1	D1	12	D28
		D1	(+/-2	(+/-2	(+/-2	(+/-2	(+/-2	(+/-3	(+/-2	(+/-3	(+/-2	(+/-3	D1	(+/-3
			days)	days)	days)	days)	days)	days)	days)	days)	days)	days)	(+/-2 days)	days)
Vital Signs	Х	Х	X	Х	Х	Х	Х	Х	Х	Х	Х	Х	Х	Χ
Height	Х													
Weight	Х	Х	Х	Х	Х	Х	Х	Х	Х	Х	Х	Х	Х	Х
ЕСНО	Х													
ECG 	Х	Х		Х		Х		Х		Х				
Gynecological Exam		X 								X				
Karnofsky Performance	Х							Х		X		Х		
Status														
CBC w/ differential, platelets 		X	X	X	X	X	X	X	X	X	X	X	X	X
Serum Chemistry 		Х	Х	Х	Х	Х	Х	Х	Х	Х	Х	Х	Х	Х
CRP, total complement, C3, C4		Х		Х		Х		Х		Х		Х		Х
Urinalysis	Х							Х		Х		Х		
TSH, free T4	Х							Х		Х		Х		
cGvHD Assessment and	Х							X		X		X		
Response Calculation 														
AE Monitoring		Thro	oughout	the stu	dy									
Concurrent Drugs	X	Thro	oughou	t the stu	ıdy									

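### The study calendar allows the stable/progressive label, which decides whether stable disease is a success, to be set after the arm is known

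*Combined protocol and SAP*

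**What the plan says.** - **Role of the label.** Sections 3.1 and 6.2.2.1 require CR or PR for a patient who enters with stable disease. For a patient who enters with progressive disease, stable disease is a success. Section 6.2.2.1 adds that the progression over the preceding 3 months must be documented.
- **Timing in Section 3.1.** "Stability will be assessed by the clinician and by the clinical exam at the screening evaluation", based on the clinician's estimate of the course over the 3 months before randomization.
- **Timing in Section 3.5.** The row "cGVHD 3 Month Trajectory (stable vs" (progressive) is marked only in the baseline/cycle 1 day 1 column. Randomization is marked only under Screening.
- **Assignment.** Section 2.5: "Randomization will be done at the time of enrollment by the Central Registration Office". Section 2.4: "Authorized staff must register an eligible candidate with NCI Central Registration Office (CRO) within 24 hours of signing consent".
- **Lists of procedures.** The nearest item in Section 2.3 is "Documentation of cGvHD diagnosis, NIH organ and global severity stage", which records severity, not trajectory. Section 2.6 opens "Following studies will be performed at the baseline before/after the enrollment and within four weeks prior to starting taking the study drug" and does not name the label. Appendix P lists neither the label nor its date.
- **Decision rule.** Section 10 selects the arm with more responses among 16 patients per arm.

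**The concern.** The same 6-month result, stable disease, is a failure under one label and a success under the other. The label rests on clinical judgement, and the documents give no criterion for grading the 3 months before entry. They describe no masking of the clinician and no matching capsules; that is read from silence. If the label is set once the arm is known, it can differ between arms for reasons unrelated to disease. The plan selects the arm with the higher count, so such a difference enters the selection directly.

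**Working it through.** **1. Order of events under each section**

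- Under Section 3.1 the label belongs to the screening evaluation. Section 2.3 requires screening studies to be complete before enrollment, and Section 2.5 randomizes at enrollment. The label then precedes the arm.
- Under Section 3.5, Randomization is in the Screening column and the label is in the next column, which is also the first dosing day. The label may then follow the arm.
- The column reading does not depend on table extraction. The trajectory row has the same blank first cell as Body Photography, a baseline item, and Randomization aligns with Informed Consent.
- No other section restores the order. The label is absent from the Section 2.3 list, the Section 2.6 list and Appendix P.
- Little trial-specific time precedes assignment: registration is due within 24 hours of consent, and "Screening procedures may be performed on a CCR screening protocol, most commonly on 04-C-0281".

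**2. The plan's own selection figures**

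Inputs from Section 10: n = 16 per arm; true rates 0.10 v 0.30 and 0.15 v 0.30. Ties are split evenly and the futility look is ignored.

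P(correct) = P(X_better > X_worse) + ½ P(tie), with X ~ Bin(16, p)

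- 0.10 v 0.30: 0.8936 + ½ × 0.0630 = 0.9250 (plan: 93%)
- 0.15 v 0.30: 0.7949 + ½ × 0.1007 = 0.8452 (plan: 84%)

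Both are reproduced.

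**3. Adding relabelled patients**

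Suppose k patients in an arm move from stable to progressive, and each gains q in the chance of success. The arm's count becomes Bin(16 − k, p) + Bin(k, p + q). The documents give neither k nor q. Assumed: k = 1 or 2, q = 0.2 to 0.6.

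| True rates | Relabelled in | k = 1 | k = 2 |
|---|---|---|---|
| 0.15 v 0.30 (0.8452) | worse arm | 0.8220 to 0.7755 | 0.7971 to 0.6912 |
| 0.15 v 0.30 | worse arm, certain success | 0.7464 | 0.6184 |
| 0.15 v 0.30 | better arm | 0.8636 to 0.9003 | not tabulated |
| 0.15 v 0.30 | both arms (range over q) | 0.842–0.847 | 0.839–0.848 |
| 0.10 v 0.30 (0.9250) | worse arm | 0.9086 to 0.8758 | 0.8902 to 0.8088 |

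Where the entries read "to", the first is q = 0.2 and the second q = 0.6. If both true rates are 0.30, the favoured arm's chance of selection goes from 0.50 to 0.5304–0.5913 (k = 1) or 0.5605–0.6793 (k = 2).

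**4. The per-arm rule**

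Section 10 needs 3 or more responses in 16 to rule out 5%. At a true rate of 5%, P(X ≥ 3) = 0.0429. If one stable-disease patient can always be relabelled as a success, 2 responses become 3 and the probability is at most P(X ≥ 2) = 0.1892. The 7-patient futility look counts only PR and CR, so the label does not affect it as worded.

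**The case against.** The strongest reply is that the text already puts the label first. Sections 3.1, 2.3 and 2.5 read together give label, enrollment, arm, which leaves one misplaced calendar mark as the evidence. A blank Screening cell is weak evidence: "CBC w/ differential, platelets" and serum chemistry are blank there too, although Section 2.3 requires them. The marked column is also headed baseline, and Section 2.6 allows baseline studies before enrollment, so the calendar does not force late labelling. All of this stands, and it limits the point to what the plan permits. It does not remove the conflict. Blood counts and chemistry are named in the screening list and the label is not. Section 2.6 also allows baseline studies after enrollment, although its wording covers the studies it lists and reaches the label only by inference.

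The label is also constrained. Section 3.1 names the clinical exam as well as the clinician's estimate, and Section 6.2.2.1 asks for documented progression. The dated clinician form (Appendix G), due at screening, holds a 3-month change rating, and Appendix P records the clinician's impression of disease activity. These reduce the room for drift and offer a partial cross-check, but none of them is the label and no rule ties them to it.

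The size is hypothetical, and its direction depends on which arm is favoured. That is correct: relabelling in the better arm raises correct selection. The even split of ties matches the plan's 93% and 84%, but Section 10 says the lower dose would likely be preferred in a tie. With equal rates of 0.30 and ties given to low dose, selection is already 57.7% v 42.3% without relabelling.

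**Conclusion.** The concern holds. Sections 3.1 and 3.5 conflict on when an endpoint-defining judgement is made, and following the calendar allows it to be made with the arm known. At 0.15 v 0.30 the loss in correct selection is about 2 to 7 percentage points for one relabelled patient in the worse arm and about 5 to 15 for two. It is close to zero when labelling leans the same way in both arms. These sizes rest on the assumed q of 0.2 to 0.6 and on one or two patients; the documents say nothing about how often relabelling would occur or which arm it would favour. The change should be made because the exposure is real and the remedy is cheap. Confidence is medium, since Section 3.1 followed as written avoids the problem. Fixing the timing deals with arm-dependent labelling only. Lenient labelling in both arms would still inflate the per-arm 3-of-16 count.

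**What to change.** - Move the trajectory row in Section 3.5 to Screening and add the item to the Section 2.3 list.
- Moving the row is not enough, because Randomization sits in the same column. Require the label, its date and the documented progression on the registration Eligibility Checklist (Section 2.4) before the Central Registration Office releases the assignment. The checklist is the right place because screening may be up to 8 weeks before enrollment.
- Add the label and its date to Appendix P.
- For patients already enrolled, take the label date from source documents, flag any dated after randomization, and compare the label with the 3-month change rating on the screening clinician form.
- Optionally, tabulate response by arm within label and repeat the selection on CR/PR only. CR/PR status is already needed for the futility look.

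**Cost:** one calendar cell, one list line, one checklist field and one Appendix P entry, with no extra visits or patients. Outside referrals may need records of the prior 3 months before registration, which could delay some. If accrual is complete, only the source-date check and the optional table apply.

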#### **Abbreviated Title:** Pomalidomide for cGvHD **Version Date:** 4/29/2025

Assessments	Screening	BL						3		6		9		
								mos		mos		mos		
		BL/	C1	C2	C2	C3	C3	C4	C5,6	C7	C8,9	C10	C11,	C12
		C1	D15	D1	D15	D1	D15	D1	D1	D1	D1	D1	12	D28
		D1	(+/-2	(+/-2	(+/-2	(+/-2	(+/-2	(+/-3	(+/-2	(+/-3	(+/-2	(+/-3	D1	(+/-3
			days)	days)	days)	days)	days)	days)	days)	days)	days)	days)	(+/-2 days)	days)
Vital Signs	Х	Х	X	Х	Х	Х	Х	Х	Х	Х	Х	Х	Х	Χ
Height	Х													
Weight	Х	Х	Х	Х	Х	Х	Х	Х	Х	Х	Х	Х	Х	Х
ЕСНО	Х													
ECG 	Х	Х		Х		Х		Х		Х				
Gynecological Exam		X 								X				
Karnofsky Performance	Х							Х		X		Х		
Status														
CBC w/ differential, platelets 		X	X	X	X	X	X	X	X	X	X	X	X	X
Serum Chemistry 		Х	Х	Х	Х	Х	Х	Х	Х	Х	Х	Х	Х	Х
CRP, total complement, C3, C4		Х		Х		Х		Х		Х		Х		Х
Urinalysis	Х							Х		Х		Х		
TSH, free T4	Х							Х		Х		Х		
cGvHD Assessment and	Х							X		X		X		
Response Calculation 														
AE Monitoring		Thro	oughout	the stu	dy									
Concurrent Drugs	X	Thro	oughou	t the stu	ıdy									

#### **Abbreviated Title:** Pomalidomide for cGvHD **Version Date:** 4/29/2025

Assessments	Screening	BL						3		6		9		
								mos		mos		mos		
		BL/ C1 D1	C1 D15 (+/-2 days)	C2 D1 (+/-2 days)	C2 D15 (+/-2 days)	C3 D1 (+/-2 days)	C3 D15 (+/-2 days)	C4 D1 (+/-3 days)	C5,6 D1 (+/-2 days)	C7 D1 (+/-3 days)	C8,9 D1 (+/-2 days)	C10 D1 (+/-3 days)	C11, 12 D1 (+/-2	C12 D28 (+/-3 days)
Skin and Oral Biopsies, saliva collection 		X								X			days)	
TBNK		Х	X	X	Х	Х	Х	Х	Х	X	Х	Х	Х	Х
Blood and urine for Immunologic Studies 		X						Х		Х		Х		Х
Blood for PK Studies 		Х	Х	Х	Х	Х	Х	Х	Х	Х				
Study drug dispensation/ return/accountability			X	X	X	Х	Х	Х	Х	Х	Х	Х	Х	Х
Rehabilitation medicine		X 								Х				
Occupational therapy Consults		X 						Х		X		Х		
Dermatology		Х								Х				
Ophthalmology		X 								X				
Schirmer's without anesthesia		X						X		X		Х		
NIH Advanced Directives form 		X												

 Clinic visits can occur  $\pm$  3 days. All procedures at protocol-driven time points are performed at the NIH Clinical Center, but if circumstances make this impossible, these data points will be collected in collaboration with referring physicians.

-  Pomalidomide at assigned doses for 6 months; another 6-month course of treatment will be allowed for patients with response (see Section **3.1.1**). Only patients who continue therapy beyond 6 months will be required to have clinical monitoring tests during cycles 7 through 12.
-  Use NIH diagnostic criteria for cGvHD (Appendix C). In addition, use Appendix D for clinical differentiation of acute versus cGvHD.
-  MRI if indicated and chest CT at baseline and if indicated, at response assessments.
-  Pregnancy tests for females of childbearing potential must follow pregnancy testing requirements as outlined in the POMALYST REMSTM program. A female of childbearing potential (FCBP) is a sexually mature female who: 1) has not undergone a hysterectomy or bilateral oophorectomy; or 2) has not been naturally postmenopausal for at least 24 consecutive months (i.e., has had menses at any time in the preceding 24 consecutive months).

Pregnancy tests must occur 10-14 days and again within 24 hours prior to initiation of pomalidomide. FCBP with regular or no menstruation must have a pregnancy test weekly for the first 4 weeks and then every 28 days while on therapy (including breaks in therapy); at discontinuation of pomalidomide and at Day 28 post the last dose of pomalidomide. Females with irregular menstruation must have a pregnancy test weekly for the first 4 weeks and then every 14 days while on therapy (including breaks in therapy), at discontinuation of pomalidomide and at Day 14 and Day 28 post the last dose of pomalidomide (see Appendix M).

-  All patients must be counseled about pregnancy precautions, risks of fetal exposure and other risks through the POMALYST REMS™ program. The counseling must be done on at a minimum of every 28 days and at drug discontinuation. See Appendix M.
-  ECG at indicated intervals baseline, at C2D1, C3D1, C4D1, C7D1 and as clinically indicated. Prolongation of QTc > 0.5 s or QTc interval increases from baseline > 0.06 s is considered as a safety concern.
-  CBC with differential and platelets, serum chemistries (including sodium, potassium, chloride, CO2, calcium, magnesium, phosphorus, blood urea nitrogen [BUN], creatinine, glucose, albumin, total protein, alkaline phosphatase, total bilirubin, AST [SGOT], ALT [SGPT], lactate dehydrogenase [LDH], and uric acid) at least every other week the first 3 months, then monthly until 9 months, then on day 28 of cycle 12. Platelets should be repeated when clinically indicated (e.g., suspected thromboembolic events).
-  Includes primary and secondary measurement of response, performance scale, global rating, and Lee Symptom Scale (Appendix G through Appendix K).
- Skin and oral biopsies and saliva collection will be performed before treatment and after 6 months of pomalidomide, with intent to sample as close to the same area as possible (Section **5.1.1**)

- Blood for Immunologic studies will be collected (Section **5.1.2**). A larger 100ml blood (12 R&G CPT) plus a 3ml theophylline citrate blood (for TGFb) will be collected only at baseline, at 3 months (beginning of cycle 4) and the 6 months evaluation (at the end of cycle 6)
- For determining serum pomalidomide levels, a 3-mL blood sample will be collected 2 hours ( $\pm$  15 minutes) after initial oral administration and repeated every 2 weeks (20-24 hours after the last oral dose and 2 hours after the dose) until the 3-month evaluation, point then monthly until the 6-month evaluation (Section 5.1.3). Pre- dosing PK can be done 18-30 hours post last dose of pomalidomide.
- Patients who discontinue study drug for any reason will be followed for survival and cGvHD course and therapy for up to 2 years from the start of study drug (see Section **6.1.3**).
- Can be done up to two weeks after starting study drug
- As indicated in section **10.3**, all subjects will be offered the opportunity to complete an NIH advanced directives form. This should be done preferably at baseline but can be done at any time during the study as long as the capacity to do so is retained. The completion of the form is strongly recommended, but is not required.

Patients may undergo additional subspecialty evaluations by Gynecology, Dermatology, Opthalmology, Dentistry, Physical Medicine and Rehabilitation and Occupational Medicine at any additional time points as indicated clinically or during the off study visit per investigator discretion.
